### 10.3 AEs

AEs reported from screening through EOS will be coded according to MedDRA® (Medical Dictionary for Regulatory Activities) version 18.1. Each reported AE will be mapped to a Preferred Term (PT) and a System Organ Class (SOC). A subset of AEs (indicated below) will be adjudicated by the independent CEC.

A TEAE will be defined as an AE that began or worsened after the time of vascular access. AEs with insufficient date or time information to determine whether or not they were treatment-emergent will be considered treatment-emergent and the ambiguity regarding start time/date for these AEs will be footnoted in summary tables.

All reported TEAEs will be listed. Separate listings will be done for deaths, non-treatment-emergent AEs and serious AEs (SAEs), treatment-emergent SAEs, TEAEs within 24 hours of IP administration (adjudicated if related to IP or procedure), and TEAEs that resulted in study discontinuation (excluding deaths). Treatment-emergent SAEs will be adjudicated. The listing of deaths will include most appropriate category of death (e.g., CV, cerebrovascular, infection, malignancy, trauma/accident) and whether or not an autopsy was performed.

Incidence and number of TEAEs will be summarized by SOC and PTs within SOCs, both overall and by relationship to IP, relationship to IP administration, and severity. Relationship status “possibly,” “probably,” or “definitely” will be considered related and will be adjudicated. Missing relationship will be considered related and missing severity will be considered severe; the lack of assigned relationships for these AEs will be footnoted in summary tables. Only the most related TEAE per subject for a given PT will be counted in summaries by relationship; similarly, only the most severe TEAE will be counted in summaries by severity. Separate summaries will be done for TEAEs within 24 hours of IP administration (adjudicated if related to IP or procedure), treatment-emergent SAEs, treatment-emergent deaths, and TEAEs resulting in study discontinuation (excluding deaths). Each summary table will include a p-value for the comparison of incidence for each SOC and PT, as well as overall, between treatment groups. Product limit estimates of median time to death and 95% CIs will be calculated.

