The secondary efficacy objective is to evaluate whether administration of CAP-1002 by intracoronary infusion may result in other left ventricular structural or functional cardiac benefits for subjects with ischemic left ventricular dysfunction and a previous MI. Also evaluations will investigate whether administration of CAP-1002 may result in clinical or biomarker benefits for subjects with ischemic left ventricular dysfunction and a previous MI.

Study Design:

In Phase 2, the Primary Randomized Cohort will enroll up to approximately 103 subjects with a previous myocardial infarction (MI) and resultant ischemic left ventricular dysfunction meeting all inclusion and no exclusion criteria. The Primary Randomized Cohort will include the Recent and Chronic MI strata (n= approximately 51-52 per stratum). These 103 subjects will be randomized in a double-blind fashion to receive either CAP-1002 or placebo (collectively referred to as Investigational Product [IP]) in a 2:1 ratio favoring CAP-1002 to achieve up to 93 subjects with complete 12 month data (assumes 10% non-completion rate and 103 subjects randomized). After completion of the screening procedures and meeting all inclusion and exclusion criteria, study subjects will be randomized to receive CAP-1002 or placebo administered via intracoronary infusion. All subjects in the Primary Randomized Cohort will be followed at week 2 and at months 1, 3, 6 and 12 after planned CAP-1002 or placebo infusion. Efficacy will be assessed at all specified post-infusion visits, with the 12 month visit being the primary efficacy endpoint. An administrative interim analysis of the final 6 month data will be performed when all subjects in the Primary Randomized Cohort have completed the 6 month visit to assist in planning Phase III studies.

The double-blind, placebo-controlled design of the Primary Randomized Cohort will maximize

the study's ability to assess both safety and efficacy, as both may be subject to bias from the perspective of Investigators and subjects.

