3 INVESTIGATIONAL PLAN

3.1 Overall Study Design and Plan

In Phase 2, the Primary Randomized Cohort will enroll up to approximately one hundred three (103) subjects with a previous myocardial infarction (MI) and resultant ischemic left ventricular dysfunction meeting all inclusion and no exclusion criteria. The Primary Randomized Cohort will include the Recent and Chronic MI strata. These approximately 103 subjects will be randomized in a double-blind fashion to receive either CAP-1002 or placebo (collectively referred to as Investigational Product [IP]) in a 2:1 ratio favoring CAP-1002 to achieve 93 subjects with complete 12 month data (assumes 10% non-completion rate). Subjects may sign consent and start the screening process immediately post-MI (e.g., acute admission at hospital). The following assessments will be permitted within 28 days immediately following the subject's MI: signing ICF, review of medical history, review of concomitant medications, and collection of laboratory samples required for assessment of study eligibility criteria (e.g., eGFR, HbA1c, hepatitis serology, HIV serology, LFTs, hematocrit, WBC, and platelet count). All other screening tests, including the subject's cardiac MRI and CT (chest, abdomen, pelvis), must be conducted greater than 28 days post-MI. Infusion must occur within 28 days of the first screening procedure that is performed greater than 28 days post-MI. Relevant safety laboratory sample collections (e.g., chemistry, hematology, urinalysis) may need to be repeated as they must be obtained within 28 days of the subject's infusion. A subject that rescreens for any reason may be required to repeat all protocol safety procedures (excluding CT of the chest, abdomen and pelvis if previously conducted) if the safety procedures were originally conducted greater than 28 days prior to the subject's infusion. A subject that rescreens for any reason may be required to repeat all protocol efficacy procedures including the cardiac MRI unless: a) the subject's efficacy procedures including baseline cardiac MRI were conducted within 28 days of infusion; or, b) the subject's efficacy procedures including baseline cardiac MRI were conducted \geq 60 days post-MI **and** within 60 days of infusion. Additional instructions are included in protocol Section 7 and Appendix I (Schedule of Events). After completion of the screening procedures and meeting all inclusion and exclusion criteria, study subjects will be randomized to receive CAP-1002 or placebo administered via intracoronary infusion. All subjects in the Primary Randomized Cohort will be followed at week 2 and at months 1, 3, 6 and 12 after planned CAP-1002 or placebo infusion. Efficacy will be assessed at all specified post-infusion visits, with the 12 month visit being the primary efficacy endpoint. An administrative interim analysis of the final 6 month data will be performed when all subjects in the Primary Randomized Cohort have completed the 6 month visit to assist in planning Phase III studies.

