7.3.6 Month 12 Visit (Day 360 ± 6 days) Procedures

Subjects will undergo multiple assessments 12 months after intracoronary infusion, including:

- Limited physical examination and cardiac physical examination
- Medication review
- Adverse events assessment
- Vital signs
- 12-Lead ECG
- Laboratory tests: hematology, chemistry, urinalysis, DSA monitoring, serum NT-proBNP; refer to [Table 1](#) for comprehensive list of laboratory tests
- Serum for biomarkers (if subject has provided consent)
- Cardiac MRI
- 24 hour ambulatory ECG recording
- NYHA functional class assessment
- Six Minute Walk Test
- MLHFQ
- SF-36 health survey
- WPAI:SHP questionnaire
- Patient Global Assessment

If subjects undergo inter-current ICD/pacemaker placement, study imaging sites must be trained and certified specifically for this protocol prior to conducting cardiac MRI in subjects with ICD and/or pacemaker placement. If subjects develop MRI contraindications, a cardiac MRI will not be performed. Such subjects will continue to be followed in the study and undergo all 12 month

study procedures except MRI. Any subject whose GFR declines to <30 mL/min during a given MRI study will not undergo contrast administration on this and subsequent MRI studies. Such treated subjects will not be withdrawn but will still be followed for inclusion in safety and efficacy analyses for other parameters assessed during the study.

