## 7.6 Study Period and Time Point Definitions

The following study periods and time points are defined:

Screening Period: the 4-week time period before IP infusion.

Baseline: the last observation of a given parameter before IP infusion of a given subject.

Day 0: the day of planned IP infusion of a given subject.

(Nominal Visit) Analysis Time Point: analysis based on data collected at the *(nominal visit)* time point, where nominal visits are as shown in the table below.

EOS, Subject Level: subject-level EOS is reached after completion of the Month 12 visit or study or discontinuation for any reason.

EOS, Study-Level: study-level EOS is reached when all randomized subjects have either completed the Month 12 visit or have discontinued from the study for any reason.

Long-Term Follow-Up (LTFUP) Period, Subject-Level: the LTFUP period begins after completion of the Month 12 visit and continues until 4 more annual visits have been completed.

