### 13.3 Final Analysis

The final analysis will occur when all subjects have reached EOS (completed the Month 12 visit or discontinued), all clinical data have been entered into the data capture system, AE and concomitant medication data have been coded, quality control checks have been completed, all

data queries have been resolved, protocol violations/ deviations have been identified, and the database has been locked.

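### SAP 10.3 plans a product-limit median time to death, but follow-up ends at Month 12, so the median will almost never be estimable; a 12-month survival estimate should replace it

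*SAP*

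**What the plan says.** SAP 10.3 closes its description of adverse-event summaries with: "Product limit estimates of median time to death and 95% CIs will be calculated". It does not say what will be shown if the median is not reached, and it plans no survival probability at a fixed time.

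The observation period is set in three places. SAP 10.3 starts: "AEs reported from screening through EOS will be coded according to MedDRA". SAP 7.6 defines the end point for each subject: "subject-level EOS is reached after completion of the Month 12 visit or study or discontinuation for any reason". SAP 13.3 puts the data cut at the same place: "The final analysis will occur when all subjects have reached EOS (completed the Month 12 visit or discontinued". The protocol schedules that visit at Day 360 with a margin of 6 days (Protocol 7.3.6), and the SAP's Month 12 analysis window runs to Day 426 (SAP 7.7).

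On completion, the protocol synopsis gives a planning figure: "assumes 10% non-completion rate and 103 subjects randomized". Neither document states an expected mortality rate.

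Other summaries of death are planned:
- SAP 10.3: a listing of deaths, and a summary of treatment-emergent deaths with a p-value.
- SAP 10.2: rates per 100 subject-years, compared with an offset for follow-up, for arrhythmic death, sudden death and MACE.
- SAP 10.1 and Protocol 9.5.1: confidence intervals for the one-month components (90% and 95% respectively).
- Protocol synopsis: 95% intervals for between-group differences in secondary safety incidence rates.

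**The concern.** A median survival time can be read from a product-limit curve only where the curve reaches 0.50. In a 12-month trial that assumes most subjects complete, the curve should stay far above that level. If so, the line in the deaths table will show a missing estimate and, in most scenarios, missing limits in both treatment groups.

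The secondary safety objective is to compare safety profiles over 12 months. All-cause death is the simplest part of that profile, yet as a separate outcome it has only counts, an incidence and a p-value. The product-limit line is the one place where the SAP would adjust all-cause death for incomplete follow-up, and it asks the curve for a quantity the follow-up is too short to supply. If this is noticed only after unblinding, the replacement estimate would be chosen post hoc.

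**Working it through.** **Inputs.** Primary Randomized Cohort of 103, with about 69 on CAP-1002 and 34 on placebo (protocol synopsis, Study Population). About 51 to 52 per MI stratum (Protocol 9.2), so roughly 34 and 17 per arm within a stratum. Non-completion of 10%, a planning assumption. The 12-month mortality m is not in the documents, so it is varied from 10% to 30%.

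**The plan's own figures.** 103 × (1 − 0.10) = 92.7, which rounds to the stated 93 completers. The 2:1 split of 103 is 68.7 and 34.3, matching 69 and 34.

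**Deaths needed.** Without early censoring, S = 1 − d/n, so S ≤ 0.50 requires d ≥ n/2: 35 of 69, 17 of 34 and 9 of 17.

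**Against the planned completion rate.** About 10 of 103 would not complete. If every one were a death, S = 1 − 10/103 = 0.90. If all 10 fell in one arm, S = 1 − 10/69 = 0.86 or 1 − 10/34 = 0.71. Only if all 10 fell in a single placebo stratum (1 − 10/17 = 0.41) would a curve cross 0.50.

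**Probability of enough deaths,** P(X ≥ n/2) with X ~ Binomial(n, m):

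| Assumed m | n=69 | n=34 | n=17 |
|---|---|---|---|
| 10% | 2e-17 | 4e-9 | 1e-5 |
| 20% | 1e-8 | 9e-5 | 0.003 |
| 30% | 0.0002 | 0.011 | 0.040 |

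**The interval.** With the log-log method, the lower limit for the median first exists at 26 deaths of 69 or 11 of 34. The probability is 9e-10 and 0.0003 at m = 10%, 0.0005 and 0.062 at 20%, and 0.11 and 0.45 at 30%. So at high mortality a lower limit could appear without a median.

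**Late-curve artefacts.** Censoring near Month 12 empties the risk set, and one late death could then pull the curve below 0.50. This was simulated with 20,000 runs per setting, exponential deaths, 10% random drop-out, and the three group sizes above. At m = 10%, the chance that the curve reaches 0.50 was 0.02% to 0.09% with last visits spread over Days 354 to 366, and 0.09% to 0.44% over Days 354 to 426. At 20%, it was at most 0.6% and 2.1%. These exceed the binomial values because late deaths among few subjects produce most of the crossings, so such a median would say little about survival.

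**How far off the median lies.** At a constant 10% per year it is ln 2 / (−ln 0.9) = 6.6 years.

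**What the same data can give.** If 12-month survival were near 95% (assumed), a simple normal half-width is 1.96 × √(0.95 × 0.05 / n): about 5 points at n=69 and 7 points at n=34. With no deaths, the exact two-sided 95% upper limit for mortality is 1 − 0.025^(1/n): 5.2% at n=69 and 10.3% at n=34.

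**The case against.** The best defence is that little depends on this sentence. It is descriptive, no hypothesis or decision rule uses it, and an entry marked not estimable is uninformative rather than wrong. That stands, and it sets the severity.

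A reader might go further and infer that the trial has no other mortality estimate with an interval, or that mortality would go unreported. The documents do not support either. The one-month death components carry intervals (SAP 10.1, Protocol 9.5.1). The protocol synopsis plans 95% intervals for differences in the 12-month secondary endpoints, and SAP 10.2 gives follow-up-adjusted rates for arrhythmic death, sudden death and MACE. The gap is narrower: all-cause death enters those analyses only inside MACE.

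A reader might also treat 10% as a ceiling on mortality. It is an assumed overall non-completion rate used for sizing. It is neither a maximum nor a per-arm figure, and it is not a death rate. The conclusion does not need it as a ceiling, since the median stays out of reach well above 10%. Nor is the median strictly impossible, as the simulation shows.

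The five-year calls do not rescue the plan. They fall after end of study, and a median at five years would need 1 − 0.5^(1/5) = 13% mortality per year.

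A last objection concerns the remedy. A log-log interval is undefined in a group with no deaths. At an assumed 5% mortality, the chance of none is 0.95^34 = 17% in the placebo arm and 0.95^17 = 42% in a placebo stratum. This is correct, and any replacement needs a rule for that case.

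**Conclusion.** The point holds in limited form. With deaths analysed to Month 12 or discontinuation, the median time to death will practically always be not estimable: even at an assumed 30% mortality it would go unreached with probability about 99.98% (n=69), 98.9% (n=34) or 96% (n=17), on the binomial calculation. At an assumed 10%, its confidence limits would be missing in both overall arms as well. This rests on the planned arm sizes and an assumed mortality range, because the documents state no rate.

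The loss is a usable censoring-adjusted 12-month estimate, with an interval, for all-cause death taken alone. It is a minor defect in one safety summary. It biases nothing and does not touch the primary safety or primary efficacy analysis.

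**What to change.** In SAP 10.3, replace the sentence on median time to death with text to this effect:

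> For all-cause death, the product-limit estimate of survival (or cumulative mortality) at Day 360 will be presented by treatment group with a 95% confidence interval, using the log-log method, or an exact binomial interval when a group has no deaths. The between-group difference will be presented with a 95% confidence interval from a method that is valid with zero events. Time runs from infusion. Subjects without a death are censored at their date of last known status (Section 8.9). Results by MI stratum are descriptive.

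The method for the difference should be named in the SAP before unblinding. Because in-window Month 12 visits start at Day 354, the number still at risk at Day 360 should be printed beside each estimate.

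The cost is a short SAP edit. It uses the same data and essentially the same procedure, and needs no extra subjects or visits.

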### 10.4 Concomitant Medications

Both general and cardiac medication use from 30 days pre infusion through EOS will be coded to generic terms using the World Health Organization Drug Dictionary (WHO-DD) version 2015:1. Listings will include IP administration date, WHO-DD drug class, WHO-DD preferred drug name, generic/trade drug name, start and stop dates, dose, route, frequency, and indication. Frequencies and percentages of subjects reporting or receiving each medication will be summarized by WHO-DD drug class and preferred name within drug class. Any pre-infusion medications reported will be listed and summarized separately from concomitant medications. Medications that were stopped no later than the day before IP administration will be considered “pre-infusion.” All other medications will be considered “concomitant.” Medications recorded

with insufficient exposure dates to determine whether or not they were concomitant will be considered concomitant.

## 10.5 Laboratory Evaluations

Listings of laboratory evaluations will include study visit, date and time of collection, normal ranges, and observed values with out-of-range values flagged. Separate series of listings will show out-of-range observations.

Observed values and changes from baseline will be summarized by study visit. Separate series of summaries will show incidence of out-of-range observations by study visit. Shift tables will summarize shifts from one out-of-range category at baseline to another out-of-range category at each subsequent study visit and will include p-values for treatment group differences.

Because local laboratories will be used for this study, units for some parameters may not be consistent across all laboratories; therefore, laboratory observations will be converted to standard units, if necessary, for summaries. [Appendix B](#) lists all clinical laboratory evaluations that will be done for this study and the corresponding standard units (evaluations listed without units are unitless).

Listings and summaries will be done separately for each of the following laboratory evaluations or groups of evaluations:

- Serum chemistry
- Hematology
- Urinalysis
- Coagulation (infusion visit only)
- Cardiac biomarkers (troponin I or troponin T, NT-proBNP)
- DSA monitoring
- ELISpot in a subset of subjects

For ELISpot, Cellular Technology Limited (CTL) will provide assay results for cells from test antigen cardiac cell lines in fetal bovine serum (FBS) containing medium, cells in serum-free medium, each in triplicate, and the positive control [phytohemagglutinin (PHA)] in a single well. Let  $X$  = average spot number to the given antigen (cells and antigen),  $SD(X)$  = SD of the three values for the antigen,  $Y$  = average spot number in the FBS-medium control (cells and no antigen), and  $SD(Y)$  = SD of the three values for the FBS-medium control. Then, the antigen specific value is:

$$X - SD(X) - [Y + 2SD(Y)]$$

A positive antigen specific response is defined as an antigen specific value  $> 3$ . All negative antigen specific values will be reported as 0 spot values since negative values are biologically irrelevant. The values of  $X$ ,  $SD(X)$ ,  $Y$ ,  $SD(Y)$ , antigen specific value, and antigen specific response will also be provided by CTL.

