## 7.7 Visit Windows

Study visits will include Screening, Day 0, and nominal week or month indicated in the table below. Visit windows will be used in data listings, summaries and analyses and will be based on study day of the observation, defined as:

$$\text{study day} = \text{date of observation} - \text{Day 0 date}$$

Visit windows per protocol and to be used in listings, summaries and analyses are as follows:

Nominal Visit	Nominal Day	Min Day Per Protocol	Max Day Per Protocol	Min Day for Analyses	Max Day for Analyses
Week 2	14	11	17	1	22
Month 1	30	27	33	23	59
Month 3	90	84	96	60	135
Month 6	180	174	186	136	270
Month 12	360	354	366	271	426

where cell entries are study days as defined above. For example, per protocol the Month 1 visit will occur between 27 and 33 days post infusion (Day 0), but for purposes of listings, summaries and analysis all observations dated between 23 and 59 days post infusion will be included in the Month 1 visit window.

Efficacy assessments that occur too late to be included in the Month 12 analysis window will be included in “last observation” analyses (see [Section 9](#)).

For ITT summaries and analyses, study day will be defined as:

$$\text{study day} = \text{date of observation} - \text{randomization date} - X$$

where X is

- for treated subjects, the number of days between randomization and IP administration.
- for untreated subjects, the median of the number of days between randomization and IP administration among treated subjects.

For example, for a subject who received IP 5 days after randomization and who had an assessment 65 days after randomization, the study day for that assessment would be 60 and the assessment would therefore fall into the Month 3 analysis window.

In addition, visit windows based on time of data collection will be defined for cardiac biomarkers as follows:

Nominal Visit	Nominal Hour	Min Hour for Analyses	Max Hour for Analyses
8 Hours Post	8	0.01	12.00
16 Hours Post	16	12.01	20.00
24 Hours Post	24	20.01	28.00

If multiple valid, non-missing observations exist within a given window, the observation to be used will be:

1. the observation closest to the nominal visit day/time in question, or
2. the latest observation if the multiple observations are equidistant from the nominal visit day/time, or
3. the average (arithmetic or geometric, as appropriate) of the observations if the multiple observations have the same actual time point.

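### The laboratory shift tables are worded to leave out normal-to-abnormal moves, and the one-value-per-window rule keeps many off-schedule peaks out of the by-visit abnormality tables

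*SAP*

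**What the plan says.** SAP 10.5 (Laboratory Evaluations) plans four kinds of laboratory output:

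- Values over time: "Observed values and changes from baseline will be summarized by study visit".
- Abnormality counts: "Separate series of summaries will show incidence of out-of-range observations by study visit".
- Shifts: "Shift tables will summarize shifts from one out-of-range category at baseline to another out-of-range category at each subsequent study visit". These tables carry p-values for treatment differences.
- Listings: out-of-range values are flagged, and "Separate series of listings will show out-of-range observations".

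SAP 7.7 (Visit Windows) assigns every post-infusion day from 1 to 426 to one of five contiguous windows. It adds hourly windows for cardiac biomarkers, centred on 8, 16 and 24 hours after infusion. It then states: "If multiple valid, non-missing observations exist within a given window, the observation to be used will be", first, "the observation closest to the nominal visit day/time in question". The latest value is used if several are equidistant, and an average if they share a time point. SAP 7.2.1 builds tables and figures by these windows. SAP 7.2.2 has listings show all data collected.

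The SAP specifies no worst post-baseline or any-time laboratory summary.

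**The concern.** A laboratory shift table exists mainly to show subjects who were normal before treatment and abnormal after it. The SAP 10.5 wording requires an abnormal category at both ends, so it leaves out exactly those subjects, and the planned p-value does not test for them.

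The window rule raises a second, independent problem. Choosing the value nearest nominal is sensible for means and changes from baseline. Applied to abnormality counts, it sets aside a value drawn off schedule, possibly because the subject was unwell, whenever another value in the window lies closer to nominal. This holds even if the off-schedule value is the abnormal one.

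What is at stake is the comparison by arm of new laboratory abnormalities and of peak enzyme release. Protocol 7.7 (Appropriateness of Measurements) names troponin and CK-MB elevations among the events to be examined more closely.

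**Working it through.** The plan gives no figure to reproduce here. The check is a count under the stated rules.

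**Shift-table cells.** Assume the usual low/normal/high categories, which give 3 × 3 = 9 cells.

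- Abnormal at baseline to a different abnormal category: low-to-high and high-to-low, 2 cells.
- If unchanged abnormal cells (low-to-low, high-to-high) are also counted: 4 cells.
- Normal-to-low and normal-to-high, the treatment-emergent shifts: 0 of 2 covered.

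The number of subjects affected depends on the share in range at baseline, which the documents do not give. Assume 70–95% for a typical analyte, with the protocol's approximate arm sizes of 69 CAP-1002 and 34 placebo. The subjects left for the shift table would be:

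- CAP-1002: 69 × 0.05 = 3.5 to 69 × 0.30 = 20.7
- Placebo: 34 × 0.05 = 1.7 to 34 × 0.30 = 10.2

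The entry criteria exclude only marked abnormalities (for example ALT above 3 times the upper limit, hematocrit below 25%, eGFR below 30), so for some analytes the in-range share could be lower than assumed.

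**Days on which an unscheduled value cannot be selected.** Suppose the scheduled draw falls within the protocol tolerance (±3 days at Week 2 and Month 1, ±6 days at Months 3, 6 and 12). Any other draw outside that tolerance is then further from nominal and is never the value used. Days affected = window width − tolerance days.

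| Window | Analysis days | Width | Tolerance days | Days affected |
|---|---|---|---|---|
| Week 2 | 1–22 | 22 | 7 | 15 |
| Month 1 | 23–59 | 37 | 7 | 30 |
| Month 3 | 60–135 | 76 | 13 | 63 |
| Month 6 | 136–270 | 135 | 13 | 122 |
| Month 12 | 271–426 | 156 | 13 | 143 |
| Total | 1–426 | 426 | 53 | 373 |

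373 / 426 = 87.6%. This is a share of calendar days, not an estimate of the share of abnormal values lost, because unscheduled draws are not spread evenly over follow-up.

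**Hourly windows.** As a hypothetical case, take a troponin of 6 times the upper limit at 4 hours and 2 times at 8 hours. Both fall in the 0.01–12.00 hour window. The 8-hour value is nearest nominal, so 2 times is tabulated. Protocol 7.4.4 treats first-day troponin elevations of up to 3 times as expected. If the reference limit is the same, the tabulated value is inside that bound and the peak is outside it.

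**Where the omitted information can still appear.**

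| Situation | By-arm output that shows it |
|---|---|
| New abnormality in the selected value | Out-of-range incidence table, not split into new and pre-existing |
| Unselected value, clinically significant and meeting the AE definition | TEAE/SAE tables (Protocol 7.4.6, SAP 10.3) |
| Enzyme peak meeting the full peri-infusion MI definition | Primary safety endpoint (SAP 2.3.1) |
| Unselected value, neither an AE nor adjudicated as an endpoint | None specified; listings only |

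**The case against.** A reader might infer that new abnormalities and unscheduled peaks vanish from the safety summaries altogether. The documents do not support that. The sentence in SAP 10.5 just before the shift-table sentence plans out-of-range incidence by visit, and Appendix C lists such tables for chemistry, hematology, urinalysis, serum biomarkers, cardiac enzymes and NT-proBNP. A subject who becomes abnormal at a scheduled visit is normally counted there.

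Other points on the plan's side:

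- **Drafting slip.** Appendix C titles the tables simply as shifts from baseline, and the literal wording would make the p-values close to meaningless. This is plausible, but SAP 10.5 is the only definition a programmer has.
- **Whole-window counting.** SAP 7.7 says "all observations dated between 23 and 59 days post infusion will be included in the Month 1 visit window", which might suggest that every value is counted. That sentence assigns values to windows. The rule for multiple values then picks the one to be used.
- **Displacement is not automatic.** An unscheduled value is used if it is the closer one or if the scheduled draw is missing. This stands.
- **Enzymes are well covered.** Three sets at about 8-hour intervals match the three hourly windows, so scheduled values are normally retained, and the 4-hour draw above is hypothetical. Peri-infusion MI is adjudicated on enzymes over the 24 hours after infusion, not on a windowed value. Appendix C also plans tables of complications within 24 hours and of TEAEs and SAEs in subjects with peri-procedural troponin elevations. This largely stands. However, the MI definition needs more than 5 times the limit plus accompanying evidence, and the SAP does not say whether a troponin elevation for those AE tables means the windowed or the peak value.
- **AE reporting catches what matters.** Often it will. It depends on the investigator's judgment, though, and Protocol 7.4.6 does not report clinically significant findings associated with the disease under study unless they are more severe than expected. That exception is relevant to troponin and NT-proBNP after MI.

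**Conclusion.** The point holds in a limited form. As worded, the shift tables and their p-values exclude both new-abnormality cells. The nearest-to-nominal rule removes an unscheduled value from the by-visit out-of-range and shift tables whenever another value in its window is closer to nominal. With the scheduled draw on time, that is certain on 373 of 426 days.

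The loss is a by-arm comparison in two places: new versus pre-existing abnormality, and peaks that were neither reported as AEs nor adjudicated. Laboratory safety reporting as a whole is not lost, since incidence tables, AE/SAE tables and full listings remain. The primary safety test uses adjudicated events and is unaffected.

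Severity is minor to moderate. The cell count assumes low/normal/high categories. The day count assumes scheduled draws within tolerance. The 70–95% in-range share is illustrative only.

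**What to change.** In SAP 10.5, define the shift tables as low/normal/high at baseline to worst low/normal/high after infusion, with in-range baselines included. Worst-low and worst-high should be tabulated separately, so that a subject with both is not forced into one cell.

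For out-of-range incidence, count a subject as abnormal if any scheduled or unscheduled value in the window is out of range. Add the 24-hour peak troponin and CK-MB by arm, and say which value defines a peri-procedural troponin elevation for the related AE tables.

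In SAP 7.7, restrict the closest-to-nominal rule to means and changes from baseline.

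The cost is SAP wording and table programming. No new samples, visits or subjects are needed.
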